### Collection, analysis and interpretation of results

Each study subject will be assigned an identification number. Only this number will be used to identify subjects in any individual tabulation. It is expected that only group data will be published. If individual subject data is to be published, no identifying information will be included. The study files will be maintained in a secure location. Access to computerized data will be restricted to IRB-approved study personnel. Password authorization will be enforced.

The study coordinator or other research team staff will provide both the FSFI and the SF-36 surveys to each subject, in paper form, upon their initiation into the study. Subjects will be given up to an hour to complete the survey by circling their responses on the paper form. The form for each subject will have the identification number as the only identifying piece of information on it. This same sequence will be performed at the other data collection points – after 6 weeks of testing (in the clinic before the 7th stimulation session) and after the 12th session. For the 6-week post-trial follow-up, a research staff will contact each subject to complete the survey over the phone, or will allow the subject to complete the survey and mail back in if they will not be visiting the clinic during that time.

As described in the appendices, each survey has a scoring method that yields a total quality of life score and a total sexual satisfaction score. These scores will be compared across the different time points as discussed above. The study team will meet with a statistical consultant (UM Center for Statistical Consulting and Research) to confirm correct approaches and conclusions. The study team will also compare the results found to other reported studies in the literature that used similar methods and analysis approaches for consistency. As described in the appendices, each survey has sub-sections that we may compare individually, if the data suggests any sub-section trends.

Data collection will be limited to the investigators and the research staff. All study personnel who have access to the data will be educated regarding the need to protect confidentiality and the procedure to be followed to ensure such protection. All staff will also be required to sign a standard medical record confidentiality agreement.

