Stimulation effects on sexual arousal are unlikely to be observed in the clinic. If this study is successful, future proposals to investigate underlying mechanisms may evaluate in vivo effects with animal models. We will have subjects complete four standard surveys as has been done for other

[figure not shown]

Figure 1. Study paradigm. Subjects will be randomized into one of two test groups (DGNS/PTNS). Sexual Function and Quality of Life surveys will be taken at study initiation and at 6-week intervals afterwards. The final 6-week period of no stimulation will look for long-term carry over.

neuromodulation studies [1], [6], [10-12]. The Female Sexual Function Index (FSFI) is a standardized survey with 19 questions on sexual health that provides a maximum score of 36 [13] (See Appendix 1 for survey). The short form 36-question (SF-36) quality of life survey was designed for general use in clinical practice [14] and will be used here to assess overall impact (See Appendix 2 for survey). The Measure of Symptoms - American Urological Association Symptom Index is a standardized 8-question survey assessing urologic concerns. The Patients' Global Impression of Change (PGIC) Scale is a 1-question survey designed to assess patients' feelings of improvement after intervention. Subjects will take the four surveys before study initiation (baseline), after each of concurrent 6-week stimulation sessions in the clinic (6weeks; 12weeks), and six weeks after study completion (long-term).

Due to the relatively small sample sizes planned for this study, we will use non-parametric statistical testing. We will use a two-sided Wilcoxon rank sum test to make comparisons of the survey scores among the different subject groups [1], [6], [8], [15], with a significance level of 0.05. FSFI and SF-36 scores will be compared for each of the potential comparisons among the baseline, 6-week and 12-week study time points and at long-term time point, for DGNS and PTNS groups separately.

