### Potential difficulties

We anticipate several potential difficulties with these planned studies. Patient compliance may be an issue, as the need to visit the clinic for 12 consecutive weeks may be a burden. We may adjust the study budget (or draw from [name] startup funds) to allocate funds to pay for daily parking (~\$7) and to give a lump sum upon completion of the study (\$50) to each subject. As other PTNS studies use weekly study durations, sometimes with much larger sample sizes, we expect that a similar willingness will occur here.

It is possible that patients find the planned stimulation amplitudes (e.g.  $PA_T$  or  $2 \times PA_T$ ) to be uncomfortable. As it is not our goal to explore optimal stimulation parameters here, we will keep current levels as low as necessary to maintain subject comfort.

It is possible that transient genital arousal or pain may occur in the clinic directly as a result of the applied electrical

[figure not shown]

Figure 3. Electrode setup for PTNS. For experimental PTNS, the TENS unit will be connected to electrodes, on either side of the ankle. Figure modified from [6].

stimulation. To protect subject privacy and modesty, we will ensure that subjects are located in private rooms and left alone for the duration of applied stimulation. Subjects will be given a method to report uncomfortable side effects if they should occur. At the conclusion of each session, we will survey subjects as to any transient pain or arousal to compare effects over time.

It is possible that patients attending [name] clinic do not have intercourse frequently enough to be eligible for the study ( $\geq 1$  time per month). If we observe that occurrence through the first month of recruitment (3 clinics) then we will relax the criteria to be a desire to have intercourse several times per month. Conversely, it is possible that subjects who have intercourse 1-2 times a month may not provide sufficient perspective on the efficacy of the stimulation for improving arousal. We will observe for this potential trend during the first 5-10 patients and will adjust the inclusion criteria threshold upwards as necessary.

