It is possible that patients may develop psychological discomfort during the research intervention. To reduce this risk, patients will be fully informed about the treatment regimen, such as the fact that they may have a doctor placing leads on their genitals every week. They will also be reminded that their continued participation is voluntary. If psychological trauma is raised, patients will be referred to our sexual health therapists for treatment. [name] is a registered nurse and sexual health therapist who does such therapy and is part of the study team.

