### Recruitment and retention

Potential subjects will be recruited from an investigator’s clinic or related clinics. Only inclusion/exclusion criteria that are provided by the patient as part of their check-in procedures or prior visits will be used to make a decision to approach a potential study subject. If a patient expresses interest in the study, then eligibility based on the full inclusion/exclusion criteria list will be verified.

The study coordinator/nurse will follow up with the patient to schedule the stimulation sessions and will administer the baseline surveys (American Urological Association Symptom Index - AUA, Female Sexual Function Index – FSFI, Short Form Health Survey – SF-36) via mail or email. Informed consent will be obtained in person at the first stimulation session, prior to any intervention. After each session, the coordinator will remind subjects of subsequent meetings.

Patient personal information will be protected per HIPAA guidelines.

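### The 6- and 12-week surveys are tied to clinic sessions with no remote route, so women who stop attending may be missing at one or both on-treatment time points

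*Combined protocol and SAP*

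**What the plan says.** *Collection, analysis and interpretation of results* has paper forms completed at study entry and then states: "This same sequence will be performed at the other data collection points – after 6 weeks of testing (in the clinic before the". The sentence goes on to name session 7, and then a further survey following session 12. *Description of methods and analysis* gives the same schedule: surveys come "after each of concurrent 6-week stimulation sessions in the clinic (6weeks; 12weeks), and six weeks after study completion (long-term"). Neither section offers another route for the two on-treatment points.

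Remote collection appears in two other places. Once the stimulation period is over, the rule differs: "a research staff will contact each subject to complete the survey over the phone, or will allow the subject to complete the survey and mail" (that is, return it by post). Baseline surveys, according to *Recruitment and retention*, go out "via mail or email".

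*Potential difficulties* expects some non-attendance: "Patient compliance may be an issue, as the need to visit the clinic for 12 consecutive weeks may be a burden". Its response is possible parking money and a possible $50, "to give a lump sum upon completion of the study". On the risk of psychological discomfort it adds: "They will also be reminded that their continued participation is voluntary". The documents do not say what happens to the surveys of a woman who stops. They also give no dropout rate, analysis set or missing-data rule.

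**The concern.** The text gives a definite collection rule, and a woman's attendance determines whether it yields data. If she stops before session 7, she has no on-treatment score. If she stops after completing the form at session 7 but before session 12, she has the 6-week score and lacks the 12-week score. No later analysis can recover a score that was never taken.

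This matters more here than in a controlled trial. *Description of methods and analysis* rules out control stimulation and compares time points within DGNS and PTNS separately, so the evidence of effect is each arm's shift from its own baseline. The protocol itself foresees visit burden, uncomfortable stimulation and psychological discomfort. If any of these makes women with poorer outcomes likelier to stop, the later time points describe a more favourable group than the baseline does. With 15 women per arm, three to five such losses are enough to matter.

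**Working it through.** **Inputs from the documents.** 15 women per arm; two-sided Wilcoxon rank sum test at 0.05; time points compared within each arm. The plan has no figure to reproduce, because it gives no dropout rate, SD or effect size.

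**Assumptions (mine).** True mean change is 0. Three of 15 (20%) or five of 15 (33%) stop. The tendency to stay has correlation ρ with a woman's own change, with 0.5 as the central value and 0, 0.3 and 0.8 for range. Baseline and follow-up scores correlate r = 0.6. Scores are normal.

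**Step 1: who is measured.**

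| Stops | Baseline | 6 weeks | 12 weeks | Long-term |
|---|---|---|---|---|
| Before session 7 | yes | no route | no route | phone or mail contact planned |
| After the session-7 form, before session 12 | yes | yes | no route | phone or mail contact planned |
| Attends all 12 | yes | yes | yes | phone or mail contact planned |

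**Step 2: bias in mean change among those remaining.** If a fraction d with the lowest tendency to stay is lost, the large-sample bias in SDs of change is ρ × φ(z_d) / (1 − d), where z_d is the normal quantile at d.

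- d = 0.20: 0.5 × 0.280 / 0.80 = 0.175.
- d = 0.333: 0.5 × 0.364 / 0.667 = 0.273.

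When exactly 3 or 5 of 15 are lost, the large-sample mean is replaced by the average expected normal order statistic of the women who remain: 0.328 for the top 12 and 0.516 for the top 10.

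- 3 lost: 0.5 × 0.328 = 0.164.
- 5 lost: 0.5 × 0.516 = 0.258.

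The two methods agree on about 0.17 to 0.26 SD of change. With 3 lost and ρ = 0.3 the small-sample figure is 0.10 (0.3 × 0.328). With 5 lost and ρ = 0.8 it is 0.41 (0.8 × 0.516). With ρ = 0 it is zero.

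**Step 3: bias in the comparison as planned.** The rank sum test is unpaired, so it can set all 15 baselines against whatever later scores exist. The bias in the mean difference, in SDs of score, is then ρ × √((1 − r)/2) × the same order-statistic mean, and √(0.4/2) = 0.447.

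- 3 lost: 0.5 × 0.447 × 0.328 = 0.073.
- 5 lost: 0.5 × 0.447 × 0.516 = 0.115.

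**Step 4: false-positive rate of the planned test.** I simulated 10,000 trials per setting, with two-sided rank sum tests of all 15 baselines against the remaining follow-up scores. At ρ = 0.5 the rejection rate was about 1.0% with 3 lost and 1.5% with 5 lost. With nobody lost it was 0.4%. Letting losses occur at random around 10% to 40%, with ρ from 0 to 0.8, gave 0.4% to 3.5% (4,000 trials per setting). The rates stay below 5% because the test ignores the positive correlation between a woman's two scores.

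**The case against.** Several stronger readings are tempting, and the documents do not support them.

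*Women who stop are never measured.* For the follow-up, the sentence just after the quoted rule says "a research staff will contact each subject to complete the survey over the phone". It is not limited to women who finished. The gap is at the two on-treatment points only.

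*The change is computed in completers.* No analysis set is stated. The planned test is unpaired, computes no within-woman change, and does not require dropping the baselines of women who left.

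*The false-positive rate is inflated.* A paired signed-rank test among those remaining would reject about 8% of the time at 20% loss and 11% at 30% loss (ρ = 0.5), but the plan does not specify that test. The specified one stays below 5% in the scenarios of step 4. This would need another look if the statistical consultant moved the plan to a paired test.

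*The 12-week point slips when sessions are missed.* That is one reading. The protocol describes 12 consecutive weeks and gives no make-up rule, so slippage is neither written in nor excluded.

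*The bias differs between arms.* Tolerability may differ between DGNS and PTNS, but the documents give no figures on it, and the stated comparisons are within each arm.

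It is also fair to say that the size and direction of any bias are assumed. The compliance problem that the protocol names is visit burden, which need not track response. It plans possible payments and current kept low for comfort. This is also a pilot that leaves control stimulation and larger samples to later studies.

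All of this narrows the claim. It does not supply an on-treatment score for a woman who stops, and a payment for completing the study gives her no survey route.

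**Conclusion.** The point stands in limited form. As written, the plan provides no way to collect the 6- or 12-week survey from a woman who is not attending, so women who stop may be missing at one or both on-treatment time points. If stopping is related to poor response or discomfort, the within-arm shift is biased towards benefit: about 0.17 to 0.26 SD of change among those remaining, or about 0.07 to 0.12 SD of score in the unpaired comparison. Both ranges assume 20% to 33% loss and a correlation of 0.5, and the second also assumes a baseline/follow-up correlation of 0.6. Both are zero if stopping is unrelated to change. The concern is the estimate, which will inform whether larger studies follow, and not the error rate of the planned test. It is worth correcting because the remedy uses means already in the protocol.

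**What to change.** In *Collection, analysis and interpretation of results*, state that every randomised woman is surveyed at weeks 6, 12 and 18 counted from her first session, however many sessions she has attended, unless she declines further contact. Women attending complete the paper form in clinic. For the others, use the mail or phone route already planned for follow-up, and record how each form was completed.

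State a short window around each date. On a weekly schedule the 7th session falls 6 weeks after the first, but the 12th falls 11 weeks after it (12 sessions, 11 weekly gaps). The window should let a form completed at the 12th session count as the 12-week survey.

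In *Description of methods and analysis*, state that all available scores are included in the woman's assigned group, and report the number surveyed at each time point by arm. A sensitivity analysis assigning zero change to women without a 12-week survey is optional.

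The cost is a wording change, a few mailed forms or calls, some forms completed remotely, and possibly a slightly smaller estimated improvement. No treatment rule changes. If all women who stop reply, each arm keeps 15 scores at each time point and the attendance-related bias disappears. Partial response would reduce it only in part.

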## Research Design and Methodology

### Design overview

We have planned a randomized pilot study to evaluate the use of two skin-surface electrical stimulation approaches for improving sexual arousal. Subjects will be assigned one of two stimulation approaches and will receive the experimental treatment during a twelve-week test period. Standard sexual function and quality of life surveys will be completed at key time points to evaluate the effects of the experimental stimulation as compared to before study initiation and to look for any long-term residual effect. Participants will also be given a demographics questionnaire once during the study, so that we can evaluate possible stratification among participants and stimulation responders.

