## Recruitment & Retention Plan

### Population characteristics

The proposal involves a 30-subject prospective study of surface electrode stimulation (dorsal genital nerve or posterior tibial nerve) weekly sessions for improving sexual arousal. As described below, adult women over the age of 18 who are neurologically stable and have intercourse at least once a month will be candidates. Typical patients will likely be in excess of 40 years of age. During each stimulation session, subjects will be reclined in a chair or examination table and will have electrodes placed at the appropriate location. After setting of parameters, stimulation will be applied for 30 minutes in duration.

We will be recruiting patients primarily from [name] pelvic pain clinic as described below. The characteristics of the patients include dyspareunia (pain with intercourse), and/or pelvic or bladder pain. The bulk of [name] pain in this clinic (~5 new patients each session, plus similar numbers of return visits) have pain with intercourse and pelvic pain as major components of their complaints. There is a sexual health therapist present in the clinic who sees most of the new patients, so we will have a psychosocial evaluation for many of them.

Patients will also be recruited from the OB/GYN clinic, other sex therapists' clinics, and UHS.

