### Inclusion criteria

- Adult women  $\geq 18$  years of age
- Sexually active  $\geq 1$  time per month ( $\geq 2$  times per month preferred)
- Having sexual dysfunction as identified by a score of 19 or less on the FSFI-6 [16].

For each question: Over the past four weeks...						
How would you rate your level (degree) of sexual desire?		Very high (5)	High (4)	Moderate (3)	Low (2)	Very low or none at all (1)
How would you rate your level of sexual arousal ("turn on") during sexual activity or intercourse?	No sexual activity (0)	Very high (5)	High (4)	Moderate (3)	Low (2)	Very low or none at all (1)
How often did you become lubricated ("wet") during sexual activity or intercourse?	No sexual activity (0)	Almost always or always (5)	Most times (4)	Sometimes (3)	A few times (2)	Almost never or never (1)
When you had sexual stimulation or intercourse, how often did you reach orgasm?	No sexual activity (0)	Almost always or always (5)	Most times (4)	Sometimes (3)	A few times (2)	Almost never or never (1)

How satisfied have you been with your overall sexual life?	Very satisfied (5)	Mod-erately satisfied (4)	About equally satisfied and dissatisfied (3)	Mod-erately dissatisfied (2)	Very dissatisfied (1)	
How often did you experience discomfort or pain during vaginal penetration?	Did not attempt intercourse (0)	Almost never or never (5)	A few times (4)	Some-times (3)	Most times (2)	Almost always or always (1)

- Neurologically stable
- Ambulatory
- Capable of giving informed consent
- English speaking
- Capable and willing to follow study procedures

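### The aim is improved sexual arousal, but the only FSFI comparison the plan commits to is the total score, so a change in the total could not be attributed to arousal

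*Combined protocol and SAP*

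**What the plan says.** All places are in the combined protocol and SAP.

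- **Aim.** Design overview describes two "skin-surface electrical stimulation approaches for improving sexual arousal". Population characteristics, Potential difficulties and the section on new methods also present arousal as the target.
- **Outcome.** Description of methods and analysis calls the FSFI a "standardized survey with 19 questions on sexual health that provides a maximum score of 36" and plans comparisons of FSFI and SF-36 scores between time points within each group. Collection, analysis and interpretation of results says which scores are meant: "each survey has a scoring method that yields a total quality of life score and a total sexual satisfaction score". The same section adds that sub-sections may be compared individually if the data point to a trend. It does not name arousal.
- **Entry.** The criterion is "Having sexual dysfunction as identified by a score of 19 or less on the FSFI-6". Arousal is one of the six items summed. Another asks: "How often did you experience discomfort or pain during vaginal penetration". Neither the inclusion nor the exclusion criteria set a condition on the arousal item.
- **Population.** Recruitment is primarily from a pelvic pain clinic. Most of its patients "have pain with intercourse and pelvic pain as major components of their complaints".
- **Decision.** The sample-size paragraph makes larger studies depend on an approach being successful. No section defines success or names a primary endpoint.

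**The concern.** A total that sums several domains does not show which of them moved. If stimulation eased pain during intercourse and did nothing for arousal, the FSFI total would still rise, and in this plan that rise would most naturally be read as support for an arousal therapy. The source clinic makes a pain route worth considering. The reference list also includes a study of tibial nerve stimulation in chronic pelvic pain, although only its title is available here.

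The error can also run the other way. A real gain in arousal is one part of a total that carries the variation of the other domains, and women who enter with high arousal have little room to show a gain.

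At stake is the decision the pilot is meant to inform, namely whether to take either approach into larger studies as a treatment for arousal. There is no control stimulation, so no between-group contrast would separate a pain effect from an arousal effect.

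**Working it through.** The plan gives no figure on this point to reproduce. It states no effect size, standard deviation or power. The check uses the item scores printed under Inclusion criteria, plus assumptions that are marked as such.

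**1. Can women with high arousal enter?** Score every item 1 to 5, as for a sexually active woman, and list all 5^6 = 15,625 answer patterns.
- Total 19 or less: 10,374 patterns.
- Of these, arousal High or Very high (4 or 5): 3,125, and 3,125 / 10,374 = 30.1%.
- Arousal Very high (5): 1,372, and 1,372 / 10,374 = 13.2%.
- Example: desire 3 + arousal 5 + lubrication 5 + orgasm 4 + satisfaction 1 + pain 1 = 19, eligible.

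These are counts of patterns and do not estimate the share of patients. The count treats all patterns as equally likely. If desire, lubrication and orgasm are assumed to lie within one point of arousal, 109 of 1,466 eligible patterns (7.4%) have arousal 4 or 5. The check establishes that such women can enter, and nothing about how many will.

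**2. Can pain alone qualify a woman?** No. With the other five items at maximum, 5 × 5 + 1 = 26. With pain and satisfaction both at 1 and the other four at maximum, 4 × 5 + 2 = 22. Both exceed 19, so every entrant falls short of the maximum on at least one further item.

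**3. How far can pain move the total?** On the FSFI-6, pain from 1 to 5 adds 4 of 30 points. One step on arousal adds 1 of 30. To translate this to the full FSFI, assume six equal domains of 36 / 6 = 6 points: 4/30 × 36 = 4.8 points for pain and 1/30 × 36 = 1.2 points for one arousal step.

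**4. Would such shifts reach p < 0.05 with 15 women in a group?** Simulation with 3,000 runs per cell, two-sided 0.05, normal scores, assumed baseline mean 18 and SD 5, and SD of change from 2 to 5:

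| Mean gain in total | Paired signed-rank, SD of change 2 / 5 | Rank sum as the plan names it, SD of change 2 / 5 |
|---|---|---|
| 1.2 | 0.55 / 0.14 | 0.00 / 0.01 |
| 2.4 | 0.99 / 0.39 | 0.06 / 0.08 |
| 3.6 | 1.00 / 0.71 | 0.40 / 0.25 |
| 4.8 | 1.00 / 0.92 | 0.84 / 0.53 |

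The test sees only the size of the gain in the total, so each row applies whichever domain produced it. Under these assumptions, a full pain response with no arousal change (4.8) would often be significant, and a one-step arousal gain with nothing else changing (1.2) would often be missed. Whether the rank sum test suits comparisons within the same women is a separate matter.

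**5. Does another measure fill the gap?** The question put after each session covers transient effects in the clinic, and the plan itself expects arousal effects not to show there. The SF-36, the urological symptom index and the global impression of change are not described as arousal measures. The sub-section clause is the only route to an arousal result, and it depends on what the data show.

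**The case against.** The strongest reply is that the full FSFI is collected at all four time points and the plan allows its sub-sections to be compared. A reader might infer that the trial is unable to address its own question. The documents do not support that, because the arousal responses will exist. What is missing is a commitment made in advance. The clause does not supply one: it is optional, is triggered by observed trends and does not name arousal. Choosing domains after seeing the trends cannot support an arousal claim.

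Other stronger readings also fail.
- A reader might infer that women without an arousal deficit will be enrolled, or are typical of this clinic. No FSFI-6 profile of the clinic is given. Arousal, lubrication and orgasm all at 4 or more occurs in only 129 of 10,374 eligible patterns (1.2%), and a score of 4 still leaves some room to improve.
- The 30.1% might be taken as a prevalence. It is not one. With no entry rule at all, the share of patterns with arousal 4 or 5 is 2/5 = 40% by construction.
- A reader might conclude that pain relief would be declared a success. No success rule exists, and SF-36 scores are compared as well.
- An entry cut-off on the arousal item might seem to follow. No particular cut-off has a basis in the documents, and the plan already has concerns about eligibility and a one-year window.

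It is also fair to say that a general sexual-function score suits an uncontrolled pilot. That justifies keeping the total. It does not justify resting an arousal conclusion on it.

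**Conclusion.** The concern holds as a mismatch between the stated aim and the committed analysis. The plan asks about arousal, commits to an FSFI total, and leaves any look at sub-sections to be prompted by the data. A rise in the total could come from less pain with arousal unchanged, and a real arousal effect could be diluted. Women with high arousal can be enrolled; how many is unknown.

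The size is conditional. The 4-of-30 and 1-of-30 contributions follow directly from the FSFI-6 items. That the full FSFI total also pools pain and arousal is inferred from those items and from the reference that calls the FSFI-6 a six-item version of the FSFI. The 4.8 and 1.2 point figures and the simulated probabilities also rest on the assumed equal domains, means and standard deviations. The case for naming the arousal measure in advance does not depend on those assumed figures. This is a cheap improvement and does not invalidate the design.

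**What to change.** In Description of methods and analysis, and in Collection, analysis and interpretation of results:

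1. Name the FSFI arousal sub-section score, before data are examined, as the measure on which any claim about arousal rests. Refer to the same measure where the sample-size paragraph speaks of an approach being successful.
2. Keep the FSFI total as a secondary measure of overall sexual function.
3. Always report the pain sub-section beside it, so that a reader can see whether pain accounts for a change in the total.
4. Describe the baseline arousal score in each group, so that any ceiling is visible.
5. Treat other sub-section comparisons as exploratory.

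The sub-section's items and scoring should be confirmed against Appendix 1. No change to the entry criteria is needed.

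The cost is protocol wording only, since the full FSFI is already completed at every time point: no new visits, questionnaires or subjects. The downside is that the sub-section has fewer items and a shorter range than the total, so it is a coarser score with more ties.
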